12.0 Potential Benefits to Subjects and Others

12.1 Potential Benefits to Subjects

Since we use a crossover design, each subject will consume placebo (no risk) and Cogni.Q (being tested for acute enhancement of two types of innate immune cells) capsules. Therefore, all subjects will be participating in both groups, and hence no subject is at a disadvantage. Furthermore, there are no known benefits to the subject from participating in this study.

12.2 Potential Benefits to Others

If the efficacy results are positive for the dietary supplement (net over placebo), the public health benefit to millions, and even billions of adults in this country and globally is self-evident. Additional studies can be designed for children and special populations (e.g., therapy-induced neutropenia patients) to assess health promotional benefit and clinical therapeutic indications.

13.0 Sharing Results with Subjects

The data of the study will not be shared with the subjects.

14.0 Subject Stipend (Compensation) and/or Travel Reimbursements

Each subject will be compensated \$25 per visit completed. (\$200 per subject if completed; total 8 visits, 1 screening visit and 7 study visits).

15.0 Economic Burden to Subjects

15.1 Costs

The cost of the comprehensive metabolic panel that is required for determination of eligibility will be paid by the study budget. These tests are being done for research purpose only and will not be billed to the subjects or their insurance company.

15.2 Compensation for research-related injury

It is the policy of the institution to provide neither financial compensation nor free medical treatment for research-related injury. In the event of injury resulting from this research, medical treatment is available but will be provided at the usual charge. Costs for the treatment of research-related injuries will be charged to subjects or their insurance carriers.

16.0 Resources Available

16.1 Facilities and locations

The study visits will be at the CTSI CRC at Hershey Medical Center, Hershey PA.

16.2 Feasibility of recruiting the required number of subjects

CTSI CRC healthy volunteer database will be used to solicit study subjects plus multiple advertising venues of trial participation opportunity will be made in Hershey and Harrisburg metro area, including CTSI website and CTSI community engagement outreach networks, Penn State STUDYfinder, local civic institutions and grocery supermarkets.

16.3 PI Time devoted to conducting the research

PI will devote 20% time. PI and study physicians will be discussing about the study progress and frequency of AE occurrences quarterly and on a need basis in between. PI will interact and coordinate with study team members through monthly meetings and on a need basis in between. PI will participate in data analyses and interpretations along with biostatistician, CO-PI and study team personnel. Study physician(s) will perform physical exam for subjects at screening, review their lab report and determine their eligibility for participation. They will be on call to answer subject's query on study related AE issues, and review AE-related entries from medication diaries.

16.4 Availability of medical or psychological resources

Medical or psychological resources at Penn State College of Medicine are available if subject needs to use them. However, subjects will be financially responsible for utilization of any resources.

16.5 Process for informing Study Team

Monthly in person meetings will be conducted. Weekly email updates will be sent to ensure the team stays well informed.

17.0 Other Approvals

17.1 Other Approvals from External Entities

Not applicable

17.2 Internal PSU Committee Approvals

Check all that apply:

Anatomic Pathology – Hershey only – Research involves the collection of tissues or use of pathologic specimens. Upload a copy of HRP-902 - Human Tissue For Research Form on the “Supporting Documents” page in CATS IRB. This form is available in the CATS IRB Library.

Animal Care and Use – All campuses – Human research involves animals and humans or the use of human tissues in animals

Biosafety – All campuses – Research involves biohazardous materials (human biological specimens in a PSU research lab, biological toxins, carcinogens, infectious agents, recombinant viruses or DNA or gene therapy).

Clinical Laboratories – Hershey only – Collection, processing and/or storage of extra tubes of body fluid specimens for research purposes by the Clinical Laboratories; and/or use of body fluids that had been collected for clinical purposes, but are no longer needed for clinical use. Upload a copy of HRP-901 - Human Body Fluids for Research Form on the “Supporting Documents” page in CATS IRB. This form is available in the CATS IRB Library.

Clinical Research Center (CRC) Advisory Committee– All campuses – Research involves the use of CRC services in any way.

Conflict of Interest Review – All campuses – Research has one or more of study team members indicated as having a financial interest.

Radiation Safety – Hershey only – Research involves research-related radiation procedures. All research involving radiation procedures (standard of care and/or research-related) must upload a copy of HRP-903 - Radiation Review Form on the “Supporting Documents” page in CATS IRB. This form is available in the CATS IRB Library.

IND/IDE Audit – All campuses – Research in which the PSU researcher holds the IND or IDE or intends to hold the IND or IDE.

Scientific Review – Hershey only – All investigator-written research studies requiring review by the convened IRB must provide documentation of scientific review with the IRB submission. The scientific review requirement may be fulfilled by one of the following: (1) external peer-review process; (2) department/institute scientific review committee; or (3) scientific review by the Clinical Research Center Advisory committee. NOTE: Review by the Penn State Hershey Cancer Institute Scientific Review Committee is required if the study involves cancer prevention studies or cancer patients, records and/or tissues. For more information about this requirement see the IRB website at:

<http://www.pennstatehershey.org/web/irb/home/resources/investigator>

18.0 Multi-Site Research

Not applicable

18.1 Communication Plans

Not applicable

18.2 Data Submission and Security Plan

Not applicable

18.3 Subject Enrollment
Not applicable

18.4 Reporting of Adverse Events and New Information
Not applicable

18.5 Audit and Monitoring Plans
Not applicable

19.0 Adverse Event Reporting

19.1 Adverse Event Definitions

For drug studies, incorporate the following definitions into the below responses, as written:	
Adverse event	Any untoward medical occurrence associated with the use of the drug in humans, whether or not considered drug related
Adverse reaction	Any adverse event caused by a drug
Suspected adverse reaction	Any adverse event for which there is a reasonable possibility that the drug caused the adverse event. Suspected adverse reaction implies a lesser degree of certainty about causality than “adverse reaction”. 
• Reasonable possibility. For the purpose of IND safety reporting, “reasonable possibility” means there is evidence to suggest a causal relationship between the drug and the adverse event.
Serious adverse event or Serious suspected adverse reaction	Serious adverse event or Serious suspected adverse reaction: An adverse event or suspected adverse reaction that in the view of either the investigator or sponsor, it results in any of the following outcomes: Death, a life-threatening adverse event, inpatient hospitalization or prolongation of existing hospitalization, a persistent or significant incapacity or substantial disruption of the ability to conduct normal life functions, or a congenital anomaly/birth defect. Important medical events that may not result in death, be life-threatening, or require hospitalization may be considered serious when, based upon appropriate medical judgment, they may jeopardize the patient or subject and may require medical or surgical intervention to prevent one of the outcomes listed in this definition.
Life-threatening adverse event or life-threatening suspected adverse reaction	An adverse event or suspected adverse reaction is considered “life-threatening” if, in the view of either the Investigator (i.e., the study site principal investigator) or Sponsor, its occurrence places the patient or research subject at immediate risk of death. It does not include an adverse event or suspected adverse reaction that had it occurred in a more severe form, might have caused death.
Unexpected adverse event or Unexpected suspected adverse reaction.	An adverse event or suspected adverse reaction is considered “unexpected” if it is not listed in the investigator brochure, general investigational plan, clinical protocol, or elsewhere in the current IND application; or is not listed at the specificity or severity that has been previously observed and/or specified.

For device studies, incorporate the following definitions into the below responses, as written:	
Unanticipated adverse device effect	Any serious adverse effect on health or safety or any life-threatening problem or death caused by, or associated with, a device, if that effect, problem, or death was not previously identified in nature, severity, or degree of incidence in the investigational plan or IDE application (including a supplementary plan or application), or any other unanticipated serious problem associated with a

19.2 Recording of Adverse Events

Research subjects will be routinely questioned about adverse events at study visits and during reminder calls for taking their capsules.

All adverse events (serious or non-serious) and abnormal test findings observed or reported to study team believed to be associated with the study capsules will be followed until the event (or its sequelae) or the abnormal test finding resolves or stabilizes at a level acceptable to the investigator.

Based on our prior clinical study experience (PK study) and the discussion about potential risks above (not higher than that of average life), we believe the monitoring plan involving PI/Study Physicians, independent monitor and Institutional Review Board (IRB) will be sufficient. Study physicians will be on-call and consulted to delineate whether an adverse event is study-related. Any reportable adverse effect will be timely reported to IRB-Hershey and other authorities including FDA (if warranted).

To minimize the possibility of minor and reversible side effects, presumably due to psychological anxiety, we will only recruit healthy participants (normal liver and kidney functions) and exclude subjects with cancer, and major cardiovascular diseases. In addition, we will closely monitor any possible side effect during the whole study section.

If emergency care is necessary during the study, our Study physician will be consulted. If the Study physician(s) determines emergency care is required, the subject will be referred/admitted to Hershey Medical Center where our Study Physicians has admitting privileges. The subject may be required to remain in the hospital for a period until the symptoms clear. Study physicians and PI will determine whether or not the event was related to the study. Study personnel will also document and report the adverse effects including but not limited to the following symptoms during the study to the IRB:

- anorexia (lack of appetite), nausea and indigestion [12].

19.3 Causality and Severity Assessments

The study physician will promptly review documented adverse events and abnormal test findings to determine 1) if the abnormal test finding should be classified as an adverse event; 2) if there is a reasonable possibility that the adverse event was caused by the study drug(s) or device(s); and 3) if the adverse event meets the criteria for a serious adverse event.

If the final determination of causality is “unknown and of questionable relationship to the study drug(s) or device(s)”, the adverse event will be classified as associated with the use of the study drug(s) or device(s) for reporting purposes. If the final determination of causality is “unknown but not related to the study drug(s) or device(s)”, this determination and the rationale for the determination will be documented in the respective subject’s case history.

19.4 Reporting of Adverse Reactions and Unanticipated Problems to the FDA

19.4.1 Written IND/IDE Safety Reports

Not applicable

19.4.2 Telephoned IND Safety Reports – Fatal or Life-threatening Suspected Adverse Reactions

Not applicable

19.5 Reporting Adverse Reactions and Unanticipated Problems to the Responsible IRB

In accordance with applicable policies of The Pennsylvania State University Institutional Review Board (IRB), the investigator will report, to the IRB, any observed or reported harm (adverse event) experienced by a subject or other individual, which in the opinion of the investigator is determined to be

(1) unexpected; and (2) probably related to the research procedures. Harms (adverse events) will be submitted to the IRB in accordance with the IRB policies and procedures.

19.6 Unblinding Procedures

Unblinding will occur at the end of the trial, upon PI's written request to IDS. In an event of AE, PI will have to give a written request to IDS for unblinding the subject, in order to figure out the treatment regime. AE will be reported to IRB. Anytime a person is unblinded and the cause will be reported to IRB by the PI.

19.7 Stopping Rules

Stopping Criteria:

- Any SAE that is considered life threatening, requires hospitalization or results in a disability/incapacitation.
- Any sickness that requires prescription medication.
- CBC: WBC counts over normal upper limit by 2 fold (i.e., 21,000 cells/ μ L) and for 2 consecutive weeks without obvious source of infection or inflammation (3,500 to 10,500 cells/ μ L).

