3.3 Early Withdrawal of Subjects

3.3.1 Criteria for removal from study

Although we expect Cogni.Q supplement-caused adverse event (AE) or serious adverse event (SAE) to be extremely unlikely, nevertheless, the clinical research staff and study physician will be responsible for detecting and documenting events that meet protocol defined criteria as an adverse event (AE) or a serious adverse event (SAE) and assist the PI in reporting.

An AE is defined as an untoward medical occurrence in a subject temporally associated with the use of a medicinal study product whether or not it is considered related to the medicinal product

An AE can be any unfavorable and unintended symptom or sign (abnormal laboratory finding) or disease temporally related to the use of a medicinal product. This can include the following:

- Exacerbation of a chronic or intermittent pre-existing condition including either an increase in frequency and/or grade of the condition
- New conditions detected or diagnosed after study treatment administration even though it may have been present prior to the start of the study
- Signs, symptoms or the clinical sequelae of a suspected interaction
- Signs, symptoms, or the clinical sequelae of a suspected overdose of either study treatment or a concomitant medication.

An SAE is defined as the following:

- Results in death
- Is life-threatening
- Requires hospitalization
- Results in disability/incapacity

Any subject who experiences an adverse event may be withdrawn from the supplement (either arm) and/or the study at any time and for any reason.

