- After Study visit #2 (Day 1), subjects will continue taking the IP capsules, that is 2 IP capsules before breakfast and 2 IP capsules before dinner, until the morning of day 21 which is **study visit #3**.
- **Study visit #3:** On Day 21, subjects will return to CRC, fasted, without taking any IP capsules. Subjects will return any unused IP capsules at this visit. Their vitals will be assessed and recorded, and will be asked questions regarding any missed doses, reason for missed dose(s), and any side effects experienced. 2.5 teaspoons of blood will be drawn (12.5 ml).
 - From Day 21 through Day 34, they will not take any IP capsules. This is the "washout" period.
- **Study visit #4:** On Day 35, subjects will return to CRC, fasted (before breakfast). Their vitals will be assessed and recorded, and will be asked questions regarding any side effects experienced during the washout period. 2.5 teaspoons of blood will be drawn (12.5 ml). Subjects will be given a refill of IP capsules. i.e. if in Group 1, a refill for placebo and if in Group 2, a refill for Cogni.Q. They will then take 2 of the assigned IP capsules and depart the clinic. They will take the other two IP capsules in the evening before dinner.
- **Study visit #5:** Day 36, subjects will return to CRC, fasted, without taking any medication. Their vitals will be assessed and recorded, and will be asked questions regarding the IP capsules, and any side effects experienced. 2.5 teaspoons of blood will be drawn (12.5 ml). They will continue to take assigned IP capsules twice (morning and evening daily) until the morning of Day 56 which is **study visit #6**.

- **Study visit #6:** Day 56, subjects will return to CRC, fasted. They will return any unused IP capsules at this visit. Their vitals will be assessed and recorded, and will be asked questions regarding any side effects experienced during the washout period. 2.5 teaspoons of blood will be drawn (12.5 ml). They will then enter the second washout phase.
- **Study visit #7:** Day 70, subjects will return to CRC, fasted, will have vitals/blood drawn (2.5 teaspoons, 12.5 ml); they will be asked about any side effects experienced during the washout period.
- A study team member will text or call weekly as a reminder to take the IP capsules.

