7.4.6.5 Prior and Concomitant Therapy

During the course of the study, prescription medicine and any medicine containing AGN are not permitted. At any point if a subject has to take prescription medication then they will be off the study.

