10.0 Data and Safety Monitoring Plan

10.1 Periodic evaluation of data

The frequency of data review for this study differs according to the type of data and can be summarized in the following table (Table 10.1.1)

Table 10.1.1

Data type	Frequency of review	Reviewer
Subject accrual (including compliance with protocol enrollment criteria)	Quarterly	PI, Independent Monitor
Status of all enrolled subjects, as of date of reporting	Quarterly	PI, Independent Monitor
Adherence data regarding study visits and intervention	Quarterly	PI, Independent Monitor
AEs and rates (including out-of-range lab values)	Quarterly	Study physicians, PI, Independent Monitor
SAEs	Per occurrence	Study Physicians, PI, Independent Monitor, IRB

❖ Independent Monitor: [name]

❖ Study Physicians: [name], Ph. D, [name] and [name]

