10.8 Suspension of research

If any unexpected serious adverse events (SAE) occur, the research will be suspended and reports will be submitted to IRB for review and other regulatory office (FDA) as appropriate.

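### On scheduled CBCs, the white-cell stopping criterion in 19.7 cannot be met before the visit that ends the dosing period in which the rise began, and nothing requires a hold or repeat CBC after a first high count

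*Combined protocol and SAP*

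**What the plan says.** The third bullet of 19.7 sets a stop for a white cell count above 21,000 cells/µL, twice the upper limit of normal, "and for 2 consecutive weeks without obvious source of infection or inflammation". It is the only laboratory criterion in that section.

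The schedule in 7.2.1 has seven CBCs: Days 0, 1, 21, 35, 36, 56 and 70. Under 7.2, capsules are taken on Days 0–20 and 35–55. At visit 3 (Day 21), "Subjects will return any unused IP capsules at this visit"; visit 6 (Day 56) does the same for period 2. The weekly calls in 10.3 ask about symptoms and involve no blood test.

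Other sections bear on a high count:
- 3.3.1 counts an abnormal laboratory finding as a possible adverse event, and a subject with an adverse event "may be withdrawn from the supplement (either arm) and/or the study at any time".
- 19.2 says that "abnormal test findings observed or reported to study team believed to be associated with the study capsules will be followed until the event" or finding resolves or stabilises.
- 19.3 says: "The study physician will promptly review documented adverse events and abnormal test findings".
- 10.3 lets the physician, with the PI, decide whether a subject with a reported event stays in the trial. 10.7 commits to judging each safety event at once and individually. 16.3 has the physicians on call.

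**The concern.** The product is being tested for raising white cells, so a persistent high count is the laboratory event that a stopping rule here should catch. The rule asks for persistence over two weeks, but no CBC is scheduled between Day 1 and Day 21 or between Day 36 and Day 56. The confirming count therefore arrives when the capsules have already run out.

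At stake is whether the prespecified rule can shorten the exposure it guards against. As written, it tells staff that one count above 21,000 is not yet a stop, and it does not say what to do next.

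**Working it through.** **Inputs.** Threshold, persistence and upper limit of normal (10,500): 19.7. CBC days: 7.2.1. Dosing days, 4 capsules a day and ±2-day visit windows, with none for the 24 h visits: 7.2. Capsules per period (84): 7.4.6.3. White-cell rise at 24 h (1.21-fold): 2.2. Section 7.4.2 gives different period 2 dosing days, but this does not move any CBC.

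**1. The plan's threshold.** 2 × 10,500 = 21,000. Reproduced.

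**2. Gaps between CBCs.** Differences of 0, 1, 21, 35, 36, 56, 70 are 1, 20, 14, 1, 20 and 14 days.

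**3. Earliest scheduled confirmation,** reading the rule as two high counts at least 14 days apart:

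| First high CBC | Confirmed | Gap (days) | Dosing status at confirmation |
|---|---|---|---|
| Day 0 (pre-dose) | Day 21 | 21 | period 1 dosing over |
| Day 1 | Day 21 | 20 | period 1 dosing over |
| Day 21 | Day 35 | 14 | period 2 about to start |
| Day 35 (pre-dose) | Day 56 | 21 | all dosing over |
| Day 36 | Day 56 | 20 | all dosing over |
| Day 56 | Day 70 | 14 | all dosing over |

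Requiring only 7 days gives the same pairs.

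**4. Visit windows.** Visits 3, 4, 6 and 7 can each shift by −2 to +2 days, and visit 5 stays one day after visit 4. That is 5⁴ = 625 schedules × 6 possible first high CBCs = 3,750 cases. In none is the 14-day criterion met before the visit that ends dosing. Those visits can fall as early as Day 19 and Day 54, but they still end dosing.

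**5. Rise first seen at visit 3, strict 14-day reading only.** Over the 5 × 5 = 25 window combinations, the gap to visit 4 runs from 10 to 18 days. It is 10, 11, 12 or 13 days in 1, 2, 3 and 4 combinations, so it is under 14 in 10 of 25. Visit 5, a day later, reaches 14 in the four with a gap of 13. In the other 6 of 25 the criterion is not met until visit 6. On a 7-day reading both counts are zero. These are counts of combinations, not probabilities.

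**6. Capsules left after a high 24 h count.** By the Day 1 (or Day 36) morning dose a man has taken 4 + 2 = 6, leaving 84 − 6 = 78. If the result is reviewed after the evening dose, 84 − 8 = 76 are left.

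**7. How large a rise is needed.** From the upper limit, 21,000 / 10,500 = 2.0-fold. The reported rise gives 1.21 × 10,500 = 12,705.

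**The case against.** The strongest reply is that nobody has to wait for 19.7. A physician who sees a count above 21,000 on Day 1 may withdraw the man or order a repeat CBC under the sections listed above. 19.7 does not confine itself to scheduled draws, and two weeks of persistence can be read as implying repeat testing. With unscheduled CBCs from Day 1 to Day 15, the present rule could be met after 15 × 4 = 60 capsules, leaving 24 of 84. All of this stands. It narrows the point to the difference between what may be done and what must be done.

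Four stronger readings are tempting and are not supported:
- *That the rule can never act.* High counts on Days 21 and 35 can meet it in time to bar period 2 or stop it at its start.
- *That the plan withholds no capsules while a hold would withhold 78.* This compares a rule without physician action against a fix that relies on it.
- *That out-of-range counts are looked at only quarterly,* as Table 10.1.1 might suggest. That row is periodic oversight. 10.7, 16.3 and 19.3 provide for immediate, as-needed and prompt review.
- *That the rule works only on the individual subject.* 19.7 does not state its level. 7.4.6.5 treats its prescription-medication bullet per subject ("At any point if a subject has to take prescription medication then they will be off the study"), whereas 10.8 acts on the trial ("If any unexpected serious adverse events (SAE) occur, the research will be suspended"). The timing result is the same either way, but on a trial-level reading a confirmed case could spare other men's capsules.

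It is also fair to say that the event is remote and that a persistence requirement is a legitimate design choice.

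**Conclusion.** The point holds as a minor, low-probability safety correction. On scheduled CBCs the criterion cannot be met during the dosing period in which the rise began, on a 14-day or a 7-day reading and across all visit windows. No section requires a hold or a repeat CBC after a first high value.

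The conclusion assumes that only scheduled CBCs are available and that windows apply to nominal days. That the event is unlikely rests on a rise seen after a single dose and on a baseline no higher than 10,500. The trial doses for 21 days, and 3.1 and 3.2 set no white-cell limit at entry, so neither is assured. The documents nevertheless give no sign that counts above 21,000 are to be expected.

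**What to change.** Replace the white-cell bullet in 19.7 with wording such as: *If WBC exceeds 21,000 cells/µL on any study CBC and no infective or inflammatory cause is evident, the subject's capsules are held (or period 2 is not started) pending study-physician review and a prompt repeat CBC, for example within 3 days. If the repeat is still above 21,000, capsules are stopped and the remaining visits continue. Otherwise the physician may release the hold.*

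The 3-day interval is a proposal, and the sponsor may choose another. The threshold and scheduled draws are unchanged, and permanent stopping still needs confirmation. A hold on Day 1 or 36 is feasible because 7.2 has the primary-aim assays run on the day of collection. A high count on Day 56 or 70, when no capsules remain, goes to follow-up under 19.2.

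**Gain.** In the best case, a count above 21,000 at 24 h, withholding up to 78 of that period's 84 capsules (76 if reviewed after the evening dose) becomes mandatory rather than discretionary. A high count at visit 3 would also be resolved before period 2 starts. Rises on Days 2–20 or 37–55 would still be seen only after dosing ends. Closing that gap would need a mid-period CBC, which is not requested here.

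**Cost.** One amended bullet, one repeat CBC per held subject and perhaps a line in the consent form. A false hold from the Day 1 evening dose through the Day 4 morning dose misses 2 + 4 + 4 + 2 = 12 of 84 capsules (14%) for that man. The sample size and analysis model do not change.
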